7.2.3.2 Shipment of Plasma Pharmacokinetic Samples

All pharmacokinetic samples should be double-bagged to contain leaks and packed with a sufficient quantity of dry ice to ensure that they remain frozen for at least 48 hours to allow for delays in shipment. All applicable shipping regulations must be followed. Shipments will be sent to the central laboratory.

7.2.3.3 Plasma Drug Assay Methodology

Plasma sample analysis will be performed at York Bioanalytical Solutions according to York Bioanalytical Solutions standard operating procedures.

Pharmacokinetic samples will be analyzed at York Bioanalytical Solutions for 5-ASA and Ac-5-ASA using validated high performance liquid chromatography methods with tandem mass spectrometric detection.

Raw data will be stored in the archives at York Bioanalytical Solutions.

Some of the plasma samples may be selected and re-analyzed and the results compared for incurred sample reproducibility. Details of the incurred sample reproducibility experiments will be provided in the Bioanalytical Study Plan.

[REDACTED]

[REDACTED]

[REDACTED]

[REDACTED]

[REDACTED]

[REDACTED]

[REDACTED]

[REDACTED]

[REDACTED]

7.2.4.1 Health-related Quality-of-Life Assessments

Daily Ulcerative Colitis Scale for Children and Caregivers

Shire has developed an electronic daily sign and symptom diary, the DUCS. Two versions have been developed: 1 patient-reported outcome (PRO) to be self-completed by children aged 8-17 years and 1 observer-reported outcome (ObsRO) to be completed by caregivers of children aged 5-10 years. Both the PRO and ObsRO will be completed by children aged 8-10 years; however, the ObsRO will be used for the secondary endpoint analysis. The data obtained from the PRO in this age group will provide information for future use to determine if children/adolescents can reliably complete the PRO.

The concept elicitation phase has informed the content of the diaries and provided for development of a draft item pool and draft measures. Cognitive debriefing interviews have been completed on these draft measures. This phase involved conducting interviews with UC patients and caregivers to evaluate the clarity, understanding, relevance, and comprehension of the draft PRO and ObsRO daily diaries as well as usability of the electronic device and feasibility of daily use at home.

Overall Current Health

An Overall Current Health item will be included in the e-diary. The Overall Current Health item has been tested in cognitive debriefing interviews with the DUCS.

PUCAI

The PUCAI is a physician-administered measure that focuses on 6 key signs and symptoms of UC and activity limitations (Turner et al. 2007). The PUCAI yields a total score ranging from 0-85 with higher scores being worse. Recommended cut-off scores to differentiate disease activity are <10 (remission); 11-30 (mild); 31-64 (moderate) and >65 (severe) (Turner et al. 2009). Evaluation of the construct validity of the PUCAI revealed that it was highly correlated with physician's global assessment of disease activity and PUCAI scores were highly predictive of the need for escalating medical therapy (Turner et al. 2009). See [Appendix 4](#).

Only sites who have executed a sublicense with Shire for PUCAI use will be able to collect PUCAI data for the study.

IMPACT III

The IMPACT questionnaire is a disease-specific health-related quality-of-life questionnaire developed for use in pediatric inflammatory bowel disease through a process of patient interviews and analysis of patient responses to an item-reduction questionnaire. This is a self-administered questionnaire, and data will be collected via paper in this study.

The IMPACT questionnaire has been studied to determine its feasibility, reliability, and validity. It was found to be a valid and reliable reflection of health-related quality-of-life of older children and adolescents with both UC and Crohn's disease (Otley et al. 2002).

In this study, the IMPACT III will be used. This is the current version of the questionnaire, adapted from IMPACT II, which was developed in 2002. The original version of IMPACT was developed in 1999. IMPACT III contains 35 items in 6 domains. The Bowel Symptoms domain and the 4 matching symptom items between the IMPACT III and the DUCS will be used to evaluate convergent validity of the DUCS.

The IMPACT is valid for children and adolescents aged 9-17 years old and is completed by the subject. Children/adolescent aged 9-17 years who cannot complete the questionnaire independently, may be assisted by an adult who is not the child's guardian or relative. Children who are 8 years old may complete the IMPACT with assistance from an adult who is not the child's guardian or relative. Children under the age of 8 years old will not complete the IMPACT.

Global Change in Health

The Global Change in Health item assesses the subject's (aged 11-17 years) or caregiver's (for children aged 5-10 years) perception of change in health since starting the study and will be administered via paper in this study. This item has been tested in cognitive debriefing interviews with the DUCS.

7.2.5 Volume of Blood to be Drawn from Each Subject

Table 6: Volume of Blood to be Drawn From Each Subject

Assessment		Sample Volume (mL)	Number of Samples: Screening	Number of Samples: Double-blind Acute Phase	Number of Samples: Open-label Acute Phase	Number of Samples: Double-blind Maintenance Phase	Total Volume (mL)
Safety	Biochemistry and β -HCG ^a	5	1	1	1	1	20
	Hematology	3	1	1	1	1	12
Pharmacokinetic samples (at participating sites only)		2	0	1	1	1	6
Total mL			8	8	8	8	32-38

^a β -HCG testing for females only.

β -HCG=beta-human chorionic gonadotropin

It is expected that approximately 32mL of blood will be drawn from subjects who participate in every phase of the study, regardless of sex and approximately an additional 6mL will be drawn from subjects participating in the pharmacokinetic section of the study. Blood sampling and volume drawn will be less for subjects who do not participate in every phase of the study, in accordance with [Table 6](#).

Note: The amount of blood to be drawn for each assessment is an estimate. The amount of blood to be drawn may vary according to the instructions provided by the manufacturer or laboratory for an individual assessment; however, the total volume drawn over the course of the study should be approximately 32-38mL. When more than 1 blood assessment is to be done at the time point/period, if they require the same type of tube, the assessments may be combined.

8. ADVERSE AND SERIOUS ADVERSE EVENTS ASSESSMENT

8.1 Definition of Adverse Events, Period of Observation, Recording of Adverse Events

An AE is any untoward medical occurrence in a clinical investigation subject administered a pharmaceutical product and that does not necessarily have a causal relationship with this treatment. An AE can therefore be any unfavorable and unintended sign (including an abnormal laboratory finding), symptom, or disease temporally associated with the use of a medicinal (investigational) product, whether or not related to the medicinal (investigational) product (International Council for Harmonisation [ICH] Guidance E2A 1995).

All AEs are collected from the time the informed consent is signed until the defined follow-up period stated in Section [7.1.5](#). This includes events occurring during the screening phase of the study, regardless of whether or not investigational product is administered. Where possible, a diagnosis rather than a list of symptoms should be recorded. If a diagnosis has not been made, then each symptom should be listed individually. All AEs should be captured on the appropriate AE pages in the eCRF and in source documents. In addition to untoward AEs, unexpected benefits outside the investigational product indication should also be captured in the AE eCRF.

All AEs must be followed to closure (the subject's health has returned to his/her baseline status or all variables have returned to normal), regardless of whether the subject is still participating in the study. Closure indicates that an outcome is reached, stabilization achieved (the investigator does not expect any further improvement or worsening of the event), or the event is otherwise explained. When appropriate, medical tests and examinations are performed so that resolution of event(s) can be documented.

8.1.1 Severity Categorization

The severity of AEs must be recorded during the course of the event including the start and stop dates for each change in severity. An event that changes in severity should be captured as a new event. Worsening of pre-treatment events, after initiation of investigational product, must be recorded as new AEs (for example, if a subject experiences mild intermittent dyspepsia prior to dosing of investigational product, but the dyspepsia becomes severe and more frequent after first dose of investigational product has been administered, a new AE of severe dyspepsia [with the appropriate date of onset] is recorded in the appropriate eCRF).

The medical assessment of severity is determined by using the following definitions:

Mild: A type of AE that is usually transient and may require only minimal treatment or therapeutic intervention. The event does not generally interfere with usual activities of daily living.

Moderate: A type of AE that is usually alleviated with specific therapeutic intervention. The event interferes with usual activities of daily living, causing discomfort but poses no significant or permanent risk of harm to the research subject.

Severe: A type of AE that interrupts usual activities of daily living, or significantly affects clinical status, or may require intensive therapeutic intervention.

8.1.2 Relationship Categorization

A physician/investigator must make the assessment of relationship to investigational product for each AE. The investigator should decide whether, in his or her medical judgment, there is a reasonable possibility that the event may have been caused by the investigational product. If there is no valid reason for suggesting a relationship, then the AE should be classified as "not related". Otherwise, if there is any valid reason, even if undetermined or untested, for suspecting a possible cause-and-effect relationship between the investigational product and the occurrence of the AE, then the AE should be considered "related". The causality assessment must be documented in the source document.

The following additional guidance may be helpful:

Term	Relationship Definition
Related	The temporal relationship between the event and the administration of the investigational product is compelling and/or follows a known or suspected response pattern to that product, and the event cannot be explained by the subject's medical condition, other therapies, or accident.
Not Related	The event can be readily explained by other factors such as the subject's underlying medical condition, concomitant therapy, or accident and no plausible temporal or biologic relationship exists between the investigational product and the event.

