Treatment-emergent adverse events considered related to investigational product will also be summarized by SOC and preferred term for Overall Safety Analysis set, Double-blind Acute and Double-blind Maintenance Phase Safety Analysis Sets, and also for Open-label Acute Phase Safety Analysis Set.

If more than 1 AE occurs with the same preferred term for the same subject, then the subject will be counted only once for that preferred term using the most severe and most related occurrence for the summarization by severity and by relationship to investigational product.

The incidence of frequently occurring TEAEs ($\geq 5\%$ of subjects in any treatment arm) will be summarized by preferred term for Overall Safety Analysis set, the Double-blind Acute and Double-blind Maintenance Phase Safety Analysis Sets, and also for Open-label Acute Phase Safety Analysis Set.

TEAEs related to investigational product, serious TEAEs, TEAEs leading to discontinuation of investigational product, and serious TEAEs leading to death will be summarized by SOC and preferred term.

Treatment-emergent adverse events of special interest (including renal toxicity, hepatic toxicity, pericarditis, myocarditis, pancreatitis, gastritis, and cholecystitis) will also be summarized by SOC and preferred term for Overall Safety Analysis set, Double-blind Acute and Double-blind Maintenance Phase Safety Analysis Sets, and also for Open-label Acute Phase Safety Analysis Set.

Renal Toxicity

- Acute renal failure - (SMQ- Broad)
- Chronic kidney disease – (SMQ- Broad)

Hepatic Toxicity

- Drug related hepatic disorders- comprehensive search – (SMQ)
- Cholestasis and jaundice of hepatic origin (SMQ)
- Drug related hepatic disorders – severe events only (SMQ)
- Liver related investigations, signs and symptoms (SMQ)
- Liver related coagulation and bleeding disturbances (SMQ)

Pericarditis

- Pericarditis (PT)
- Pleuropericarditis (PT)

Myocarditis

- Myocarditis (PT)
- Allergic Myocarditis (PT)
- Eosinophilic myocarditis (PT)

Pancreatitis

- Acute pancreatitis (SMQ)

Gastritis

- Gastrointestinal nonspecific inflammation (SMQ)
- Gastrointestinal nonspecific dysfunction (SMQ)

Cholecystitis

- Cholecystitis (PT)
- Cholecystitis acute (PT)
- Cholecystitis chronic (PT)
- Cholecystectomy (PT)
- Cholecystocholangitis (PT)

Subject listings will be presented for all deaths, serious AEs (SAEs), and subjects withdrawn due to AEs.

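### Protocol 8.1.2: the guidance table's bar for a related adverse event is stricter than the paragraph it supports, and neither document says which prevails

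*Protocol*

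**What the plan says.** Protocol 8.1.2 uses a two-level scale, Related or Not Related, and describes it twice.

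- **Paragraph.** An event is related "if there is any valid reason, even if undetermined or untested, for suspecting a possible cause-and-effect relationship" with the product. For the other level: "If there is no valid reason for suggesting a relationship, then the AE should be classified as" not related. Whether something else could also explain the event plays no part.
- **Table, Related row.** The timing must be compelling and/or the event "follows a known or suspected response pattern to that product, and the event cannot be explained by" the subject's condition, another therapy or an accident.
- **Table, Not Related row.** Two conditions are joined. One is a ready alternative cause: "The event can be readily explained by other factors such as the subject's underlying medical condition, concomitant therapy, or accident". The other is the absence of any credible link to the product in time or biology.

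The table is offered as further guidance that might help, but its column is headed as the definition of relationship. No sentence in either document ranks the two texts.

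The classification is used in four places:

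- SAP 5.9.1: "Treatment-emergent adverse events considered related to investigational product will also be summarized by SOC and preferred term", for the overall set and for each phase. Protocol 9.9 plans the same kind of summary.
- Protocol 8.2.7: notification of authorities, IRBs and ECs, and active sites covers SAEs that are both related and unexpected.
- Protocol 8.2.4: an SAE discovered after the study has ended must be reported if it is considered related.
- SAP 8.9: a missing relationship for a TEAE is set to Related. The SAP gives no definition of relatedness of its own.

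Protocol 7.1.3, on entry to the Open-label Acute Phase, speaks of events possibly or probably related. Those grades do not exist in 8.1.2.

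**The concern.** For an oral 5-ASA given to children with UC, an event with two candidate causes is not far-fetched. Protocol 8.1.4 makes significant worsening of UC symptoms an adverse event, so it needs a causality call. The SAP's events of special interest include hepatic toxicity, pancreatitis and nonspecific gastrointestinal inflammation or dysfunction. The sponsor therefore regards these as relevant to the drug, and some overlap with the disease. The Amendment 4 rationale in the protocol history itself links UC with primary sclerosing cholangitis, so a raised liver enzyme can have a disease explanation as well as a drug one.

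These are the events on which the two texts part. If sites differ in the text they follow, the same clinical event is coded differently from site to site. The table's extra condition pushes towards fewer related events, which is the less cautious direction. It also runs against the SAP, which resolves a missing relationship towards Related.

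**Working it through.** The plan gives no figure to reproduce. The check is to classify every combination under each text.

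**Inputs** (all from Protocol 8.1.2):

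- A: is there a valid or plausible reason to suspect the product?
- B: can disease, other therapy or accident explain the event?
- Paragraph: related if A is yes, not related if A is no.
- Table: Related needs A (compelling timing or a response pattern) and not B. Not Related needs B and not A.

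| A: drug link | B: other explanation | Paragraph | Table |
|---|---|---|---|
| yes | no | related | Related, if the link is compelling or follows a pattern |
| no | yes | not related | Not Related |
| yes | yes | related | neither row |
| no | no | not related | neither row |

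1. The paragraph covers all 4 combinations. The table covers 2 and leaves 2 open.
2. The third row carries the concern. The event fails Related because another explanation exists ("and the event cannot be explained by the subject's medical condition, other therapies, or accident"). It fails Not Related because that row requires that "no plausible temporal or biologic relationship exists between the investigational product and the event".
3. In the fourth row the paragraph gives not related and the table gives nothing. This gap matters less, since the paragraph's answer involves no drug suspicion.
4. In the first row the thresholds also differ. A valid but less than compelling reason, with no known or suspected response pattern, is enough for the paragraph but not for the table.

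**Possible size.** Let x be the share of TEAEs in the third row, and f the fraction of those that sites record as not related because of the table. The related share of TEAEs then falls by f × x. The documents give neither x nor f. If x is assumed to lie between 10% and 40%, the fall is between 0 (f = 0) and 10 to 40 percentage points (f = 1). The f = 1 figure is an upper bound. It needs every such event to be coded not related, although the table's own Not Related row does not fit these events.

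**Sensitivity of the tables to a single call.** SAP 3.5 puts the Double-blind Acute Phase at 53 subjects, so 53 / 2 = 26.5 per arm. One subject moved between related and not related changes an arm's incidence by 1 / 26.5 = 3.8 percentage points. With 80 subjects in the Double-blind Maintenance Phase (the stated minimum), it is 1 / 40 = 2.5 points. About 48 sites are planned (Protocol 3.3), and randomization is stratified by weight group, not by site (Protocol 6.2.2). Differences in how sites read 8.1.2 are therefore not balanced by stratification.

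**The case against.** The strongest reply is that the paragraph governs. It says how the investigator should decide, while the table is only offered as possibly helpful. An investigator who finds that neither row fits would naturally return to the paragraph and record the event as related. This has weight: the paragraph is the better candidate for the operative rule. It does not settle the matter, because no precedence is stated and the table is headed as a definition.

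Other safeguards also stand:

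- Protocol 8.1.4 keeps UC symptoms within normal fluctuation or expected progression out of the adverse event data. This narrows the affected events.
- Protocol 8.2.2 and 8.2.4 require all in-study SAEs to be reported within 24 hours whatever their relationship.
- The SAP tabulates all TEAEs, serious TEAEs, TEAEs leading to discontinuation and events of special interest without filtering on relatedness. Possible 5-ASA intolerance stays visible there.

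A reader might infer three stronger things, and the documents support none of them:

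- **That events with two candidate causes cannot be classified at all.** This is true of the table only; the paragraph classifies every event.
- **That related counts simply measure site habit, or shift by a known amount.** No rates are given, and the shift depends on an unknown f.
- **That the comparison of doses is biased.** Both double-blind arms use the same text, the dose is masked and allocation is 1:1, so the expected effect is noise and a lower absolute count. In the Open-label Acute Phase the dose is known, but all subjects receive the high dose, so no dose comparison is made within that phase.

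**Conclusion.** Section 8.1.2 contradicts itself as written. The guidance table sets a stricter test for Related than the paragraph it is meant to support, and nothing in the protocol or SAP ranks them. The consequence is limited:

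- **Exposed:** the related-TEAE summaries, which could be noisy or too low; onward reporting of related, unexpected SAEs; and reporting of SAEs found after the study.
- **Not exposed:** initial capture of in-study SAEs and the tables of all TEAEs.

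The numerical size cannot be derived from the documents. The 10 to 40 point figures are upper bounds on an assumed range, not estimates. The conclusion assumes only that some sites will consult the table. It is worth correcting because the remedy is small and the discrepancy runs in the less cautious direction, but it does not threaten the trial's main comparisons.

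**What to change.** **Preferred.** Make the table follow the paragraph. In the Related row, delete "and the event cannot be explained by the subject's medical condition, other therapies, or accident" and bring the rest of the row to the paragraph's standard of a reasonable possibility. Define Not Related as no reasonable possibility of a link. Both open combinations are then classified, and they agree with the paragraph.

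**Minimum.** Add one sentence stating that the paragraph prevails where the table differs.

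With either option, notify sites. Also reconcile the possibly or probably related wording in Protocol 7.1.3 with the two-level scale. Which events bear on open-label entry is for the sponsor to settle.

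**Cost.** Rewriting two rows means a protocol amendment with IRB/EC approval (Protocol 10.3.2) across about 48 sites in about 8 countries, in a study already at Amendment 5 (April 2017) and planned to run from 2013 to 2018. The single sentence is a smaller change to the text. Slightly more events would be classed as related. A mid-study change could also create a before/after difference in causality coding, so the date of the change should be recorded and noted beside the related-TEAE tables. No dose, visit or endpoint changes.

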8.1.3 Outcome Categorization

The outcome of AEs must be recorded during the course of the study in the eCRF. Outcomes are as follows:

- Fatal
- Not Recovered/Not Resolved
- Recovered/Resolved
- Recovered/Resolved With Sequelae
- Recovering/Resolving
- Unknown

8.1.4 Symptoms of the Disease Under Study

Symptoms of the disease under study (eg, episodes of diarrhea with blood and mucus, abdominal pain, and urgency) should not be classed as AEs as long as they are within the normal day-to-day fluctuation or expected progression of the disease and are part of the efficacy data to be collected in the study; however, significant worsening of the symptoms should be recorded as an AE.

8.1.5 Clinical Laboratory and Other Safety Evaluations

A change in the value of a clinical laboratory, or vital sign, assessment can represent an AE if the change is clinically relevant or if, during treatment with the investigational product, a shift of a parameter is observed from a normal value to an abnormal value, or a further worsening of an already abnormal value. When evaluating such changes, the extent of deviation from the reference range, the duration until return to the reference range, either while continuing treatment or after the end of treatment with the investigational product, and the range of variation of the respective parameter within its reference range, must be taken into consideration.

If, at the end of the treatment phase, there are abnormal clinical laboratory, or vital sign, values which were not present at the pretreatment value observed closest to the start of study treatment, further investigations should be performed until the values return to within the reference range or until a plausible explanation (eg, concomitant disease) is found for the abnormal values.

The investigator should decide, based on the above criteria and the clinical condition of a subject, whether a change in a clinical laboratory, or vital sign, parameter is clinically significant and therefore represents an AE.

Subjects with liver enzymes (alanine aminotransferase, aspartate aminotransferase, gamma-glutamyl transferase) elevated beyond twice the upper limit of normal will be further evaluated with a panel of tests assessing markers of hepatic injury, inflammation, and function. At a minimum, this panel should include the following: repeat alanine aminotransferase, aspartate aminotransferase, gamma-glutamyl transferase, total and direct bilirubin, serum albumin, lactate dehydrogenase, and prothrombin time. Consideration should be given as to whether an arterial blood sample for serum ammonia should also be obtained based on the magnitude of transaminase elevation and the subject's clinical status (such as presence of mental status changes or other findings that might suggest Reye's syndrome; the Shire Medical Monitor should be consulted prior to collection of this specimen). Subjects should be followed until their hepatic enzyme values return to normal ranges. If abnormal values persist for greater than 1 week, the Shire Medical Monitor should be contacted for discussion and agreement of additional etiology investigation.

